### **Treatment Protocol:**

## **Initial Assessment (2 hours)**

\*\*Prior to the Initial Assessment, enrolled participants will receive an email from the study coordinator outlining the requirements of the clinically defined "off" state.

Outcome Measures: At the first study visit, Outcome Measure (OM) assessment will be conducted for ALL participants. Outcome measures (all previously validated in PD) will include the following:

### **Physical Assessments:**

1. MDS-UPDRS - Movement Disorder Society's Unified Parkinson's Disease Rating Scale (MDS-UPDRS) Part III is a comprehensive clinical assessment tool designed to evaluate the motor function in patients with Parkinson's disease. This segment of the scale involves a clinician-scored evaluation of motor skills, which includes assessments of speech, facial expressions, tremors, rigidity, finger dexterity, hand movements, rapid alternating movements, leg agility, arising from a chair, posture, gait, postural stability, and body bradykinesia. The UPDRS will be administered by a Movement Disorder Society-certified assessor.
2. 6-minute walk test (6MWT) - The 6-minute walk test (6MWT) is a simple, commonly used test to assess exercise capacity and functional mobility in individuals with Parkinson's Disease. During the 6MWT, the participant will be asked to walk as far as possible for six minutes in a straight line along a flat, hard surface. The participant's heart rate, blood pressure, and oxygen saturation will be monitored during the test. The distance that the participant is able to walk within the six minutes is recorded and is used as a measure of exercise capacity and functional mobility.
3. 10-Meter Walk Test (10MWT) - The 10 meter walk test (10MWT) is a clinical assessment tool used to measure gait speed in individuals with PD. The test is used to evaluate the functional mobility and gait speed of patients. During the 10MWT, the participant will be asked to walk a distance of 10 meters (about 33 feet) at their usual walking speed. The time it takes to complete the distance is recorded and the gait speed is calculated by dividing the distance by the time taken to complete it.
4. Mini-Balance Evaluation Systems Test (Mini-BESTest) - The Mini-BESTest (Balance Evaluation Systems Test) is a standardized, performance-based assessment tool used to evaluate balance and mobility in individuals with PD. It is designed to assess multiple aspects of balance, including anticipatory postural adjustments, reactive postural control, sensory orientation, stability in gait, and dynamic balance during functional tasks. The Mini-BESTest consists of 14 items, including tests of static and dynamic balance, sensory integration, and gait. The test takes approximately 15-20 minutes to administer.
5. Functional Gait Assessment (FGA) - The Functional Gait Assessment (FGA) is a standardized evaluation tool used to assess an individual's gait, balance, and risk of falling. This 10-item test evaluates walking ability under various conditions, including walking with a narrow base of support, walking with eyes closed, walking backwards, and changes in gait speed.
6. Modified Clinical Test of Sensory Integration and Balance (mCTSIB) - The CTSIB (Clinical Test of Sensory Integration of Balance) is a clinical assessment tool used to evaluate the ability of an individual to maintain balance under different sensory conditions. The test assesses the integration of sensory information from the visual,

somatosensory, and vestibular systems that are necessary for maintaining postural stability and balance during standing and walking. During the CTSIB test, the participant will be asked to stand on a firm or foam surface with their eyes open or closed. The test administrator observes the participant's postural sway and records their ability to maintain balance.

### **Cognitive Assessments:**

1. Delis-Kaplan Executive Functioning System (DKEFS) Trails Test - The Delis-Kaplan Executive Function System (DKEFS) is a neuropsychological test battery that assesses various aspects of executive function, including cognitive flexibility, inhibition, and problem-solving. The trails test assesses visual attention and task switching. Participants will be asked to draw lines connecting numbers and letters in sequential order as quickly and accurately as possible.
2. Delis-Kaplan Executive Functioning System (DKEFS) Color Word Interference Test - The Color Word Interference test assesses selective attention and response inhibition. Participants will be asked to name the ink color of printed words while inhibiting automatic reading of the word itself.
3. Delis-Kaplan Executive Functioning System (DKEFS) Verbal Fluency Test - the Verbal Fluency Test assesses language-based executive function. Participants will be asked to generate as many words as possible within a given category (e.g., animals) or starting with a specific letter. These tests are commonly used in clinical settings to assess executive function and may help detect potential cognitive impairments or changes in cognitive function over time.
4. Digit Span Memory Test (DSMT) - The Digit Span Memory Test is a neuropsychological test that assesses working memory. Participants will be presented with a series of numbers and asked to repeat them back in the same order (Digit Span Forward) or in reverse order (Digit Span Backward). The test takes approximately 5-10 minutes to complete
5. Digit Symbol Substitution Test (DSST) - The Digit Symbol Substitution Test (DSST) is a neuropsychological test that assesses cognitive processing speed and attention. Participants will be presented with a series of symbols paired with digits and asked to match as many symbols to their corresponding digits as possible within a set time limit. The test takes approximately 5-10 minutes to complete.
6. MoCA - The Montreal Cognitive Assessment (MoCA) is a brief screening test that assesses various cognitive domains, including attention and concentration, executive functions, memory, language, visuoconstructional skills, conceptual thinking, calculations, and orientations. The MoCA is used to detect mild cognitive impairment (MCI), a condition that can precede the onset of dementia and monitor changes in cognitive function over time.
7. Flanker test - The Flanker test is a cognitive task designed to measure attention and inhibitory control abilities. This test will be performed on an iPad or computer, and will measure reaction time (how quickly participant respond to stimuli), and accuracy. It provides insight into how well the participant can maintain attention on a central task while ignoring distracting information. This test will take approximately 5-10 minutes to administer. Results will be used to assess the effectiveness of the exercise intervention.

### **Questionnaires:**

1. PROMIS-NeuroQOL questionnaires - The Patient-Reported Outcomes Measurement Information System (PROMIS) NeuroQOL is a questionnaire designed to assess health-related quality of life as it relates to cognitive function. Participants will be asked to complete a series of questions related to cognitive abilities such as memory, attention, and processing speed. The questionnaire takes approximately 10-15 minutes to complete and is administered by a trained healthcare professional. The results of the PROMIS-NeuroQOL may help identify potential cognitive impairments or changes in cognitive function over time.
2. Short Form-36 (SF-36) - The SF-36 is a questionnaire designed to assess health-related quality of life. Participants will be asked to answer questions related to their physical and mental health, including their ability to perform daily activities, their level of pain and discomfort, and their emotional well-being. The questionnaire takes approximately 5-10 minutes to complete and is administered by a trained healthcare professional. The results of the SF-36 may help identify areas of concern and inform healthcare providers about the participant's overall health status. Results will be used to assess the effectiveness of the exercise intervention.
  1. In the case of identification of severe depression or risk, the research team member administering the questionnaire will immediately notify the principal investigator. The principal investigator or a suitably qualified co-investigator will then review the participant's responses to confirm the initial assessment. If the investigator agrees with the initial assessment, they will notify the participant's clinician about the situation within 24 hours, or as soon as possible if the risk appears immediate. We will inform the participant about our concerns and our intention to contact their clinician.

#### **Blood Draw:**

- -In order to investigate the presence of the Val66Met polymorphism in our participants, we will collect a blood sample (10mL or 2 teaspoons) for genetic analysis.
- -Trained phlebotomists will collect approximately 10 ml (2 tablespoons) of blood from each participant using standard venipuncture techniques.
- -The blood samples will be stored securely and transported to a laboratory for analysis using polymerase chain reaction (PCR) and/or sequencing methods to determine the presence or absence of the Val66Met polymorphism.

*Participants will be compensated with a \$100 clincard at the conclusion of this visit.*

#### **Treatment (over the course of 4-6 weeks, 1 hour sessions, up to 3 sessions/week)**

- During treatment clinic visits, participants who are randomized into the **active taVNS + exercise** group will receive 15 minutes of active taVNS prior to treatment.
- Participants who are randomized into the **non-active taVNS + exercise** group will receive 0 mA of current for 15 minutes prior to treatment.
- To implement the non-active condition, participants will still undergo the same electrode placement procedure as those in the active taVNS group, with the electrodes placed in the ears. However, the taVNS device will be set to a 0 mA (no stimulation) during the non-active condition. Participants will be informed prior to the stimulation that they may or may not feel anything during the session, and that just because they do not feel anything does not mean that they are not receiving stimulation.

- All participants will be guided through low intensity, high amplitude exercises led by a trained exercise specialist.
- The exercise intervention proposed involves the supervision of a trained exercise specialist at all times during the treatment session
- The use of a gait belt will further ensure the participant's safety by providing additional support and stability during exercise
- The proposed exercise intervention will be conducted by a trained exercise specialist who has expertise in assessing and managing potential risks associated with exercise interventions. This will ensure that the intervention is safe for the participant and will minimize the risk of injury or adverse events
- After each treatment session, participants will be asked post-intervention questions to evaluate potential side effects of the taVNS treatment and exercise (see below):
  - 1. Since our last session, have you experienced any unusual physical symptoms such as dizziness, fatigue, muscle soreness, shortness of breath, or heart palpitations?
  - 2. Have you experienced any unusual discomfort or pain in the ear where the taVNS device was applied?
  - 3. Have you noticed any changes in your skin around the area where the taVNS device was applied, such as redness, swelling, or rash?
  - 4. Have you felt any changes in your mood, like feeling more anxious, depressed, or irritable since the last session?
  - 5. Have you noticed any changes in your ability to concentrate or remember things?
  - 6. Have you experienced any other side effects or symptoms that you believe may be related to the taVNS treatment or exercise program?
- If a participant reports experiencing any adverse effects, they will be advised to seek appropriate medical attention. We will also document all reported side effects.
- Participants will wear a heart rate monitor during each treatment session to monitor and record heart rate response to exercise.
- Participants will be asked to answer a series of questions about the tolerability of the taVNS treatment & exercise intervention via a RedCap survey.

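### Side-effect items 1 and 4 look back to the last session but are scheduled after the next one, so the onset of between-session symptoms cannot be placed

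*Combined protocol and SAP*

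**What the plan says.** In the combined protocol and SAP, the Treatment section puts the stimulation first: the active group "will receive 15 minutes of active taVNS prior to treatment", and the non-active group has the same electrode placement at 0 mA for the same time. Exercise follows. The side-effect questions come last: "After each treatment session, participants will be asked post-intervention questions to evaluate potential side effects of the taVNS treatment and exercise".

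Two of the six items carry a look-back window:

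- Item 1: "Since our last session, have you experienced any unusual physical symptoms such as dizziness, fatigue, muscle soreness, shortness of breath, or heart palpitations".
- Item 4: "Have you felt any changes in your mood, like feeling more anxious, depressed, or irritable since the last session".

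The other four give no window. Items 2 and 3 concern the device site: "Have you experienced any unusual discomfort or pain in the ear where the taVNS device was applied" and "Have you noticed any changes in your skin around the area where the taVNS device was applied, such as redness, swelling, or rash". Item 5 asks "Have you noticed any changes in your ability to concentrate or remember things". Item 6 names both interventions together: "Have you experienced any other side effects or symptoms that you believe may be related to the taVNS treatment or exercise program".

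Reported effects are to be documented, and the participant is advised to seek medical attention. The Statistical Analysis section lists adverse events among the feasibility measures to be tracked.

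**The concern.** The time of asking and the period asked about do not fit together. A question about the days since the previous visit is normally put when the participant arrives. Here it is put once that day's stimulation (or 0 mA) and exercise are over. Dizziness, palpitations or low mood during the interval would therefore not be asked about by script until the participant had been through another session. By then, a yes to item 1 could refer to the days at home, to that day's taVNS or to that day's exercise.

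What is at stake is the quality of the adverse-event record. It is one of the few results this feasibility study commits to report. A record without onset times cannot show whether a given person's symptom followed stimulation, followed exercise or appeared later at home.

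**Working it through.** The plan gives no figure to reproduce. The check sets the texts side by side and then counts the intervals affected.

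**Step 1. Window and attribution, item by item (all asked after the session).**

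| Item | Look-back window | Source of symptom separated? |
|---|---|---|
| 1 Physical symptoms | Since last session | No |
| 2 Ear pain | None | Yes, device site |
| 3 Skin change | None | Yes, device site |
| 4 Mood | Since last session | No |
| 5 Concentration, memory | None | No |
| 6 Other | None | No, taVNS and exercise joined |

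The mismatch between window and time of asking applies to items 1 and 4. Items 5 and 6 are undated and do not separate sources, which is a lesser form of the same weakness.

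**Step 2. The two readings of the window.**

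- *Last session means the previous visit.* The interval is covered, but is first asked about after the next exposure, and the answer also takes in that day's session.
- *Last session means the one just finished.* The window runs from the end of the session to the question. The days between visits may never be asked about.

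Staff could apply either reading, so answers might not be comparable between participants or visits.

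**Step 3. The two ends of the schedule.** At session 1 there is no earlier session to refer to. After the final session, neither Re-Assessment nor Follow-up describes a further round of these items, so the last interval has no scripted question.

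**Step 4. Does another provision cover the interval?** The heart rate monitor records the response to exercise during the session. The RedCap tolerability survey has no stated content and, within the treatment period, no stated timing. The interview takes place at re-assessment. The 5-minute tolerance trial is a single screening step. None is a scripted symptom question on arrival.

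**Step 5. Count.** Inputs: 4 to 6 weeks and up to 3 sessions per week (Treatment heading); up to 20 participants (Patient Population). Three per week is a ceiling. The lower value of 1 per week is an assumption.

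Sessions = weeks × sessions per week. Intervals = sessions − 1. Trial total = intervals × 20.

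| Sessions per week | Weeks | Sessions | Intervals per person | Total for 20 |
|---|---|---|---|---|
| 1 (assumed) | 4 | 4 | 3 | 60 |
| 1 (assumed) | 6 | 6 | 5 | 100 |
| 3 | 4 | 12 | 11 | 220 |
| 3 | 6 | 18 | 17 | 340 |

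The totals assume full enrollment and attendance. They count calendar intervals, not symptoms or late reports.

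**The case against.** The best defense is that the wording is loose rather than wrong. The plan does not say the questions come immediately after the session, and asking items 1 and 4 at the start of the next visit would suit their wording. The questionnaire is also not the only channel. A trained exercise specialist supervises throughout, heart rate is monitored, and the provision for reported adverse effects is not limited to scripted answers, so a participant may speak up on arrival. All of this stands, and it limits the point to what the script does. It does not remove the point, because a plan that can be read as asking before the next session or after it has not settled the matter.

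Four stronger readings are tempting, and the documents do not support them.

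- *Every participant is stimulated again before being asked.* The non-active arm receives 0 mA. It repeats only electrode placement and exercise.
- *All side effects are merged into one answer.* There are six items, and items 2 and 3 isolate ear and skin effects at the device site.
- *Stimulation effects cannot be separated from exercise effects.* Both arms have the same electrode placement, exercise and question schedule and differ in current, so the arms can still be compared at group level. What is lost is timing and attribution within a person. The Statistical Analysis section speaks only of tracking adverse events, and with at most 20 participants a group contrast would not recover onset.
- *The participant is left unprotected, with 340 late reports.* Spontaneous reporting and supervision remain, and 340 is the ceiling on intervals, not a count of events.

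**Conclusion.** The point holds in a limited form. Items 1 and 4 have a look-back window that does not match the time at which they are asked, and no earlier symptom question is described. Followed literally, the plan first asks about a between-session symptom after the next session or, on the other reading, may not ask about it at all. The first session and the final interval are also left without a workable question.

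The consequence is weaker onset timing and within-person attribution in the adverse-event record. The comparison of active with 0 mA is not biased by this, and device-site effects are already identified. The mismatch recurs at 3 to 17 intervals per participant, assuming 1 to 3 sessions per week. The absence of an arrival check is inferred from the plan's silence. The point is worth correcting because it recurs at every interval and costs little to put right.

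**What to change.** Reconcile the time of asking with the period asked about, keeping the existing items:

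1. Ask the since-last-session items (1 and 4) on arrival, before electrodes are placed, from session 2 onward.
2. Ask them once more at re-assessment, to cover the interval after the final session.
3. Keep the post-session round, with wording limited to that day's session.
4. Record the time point with each report.

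A further round between stimulation and exercise would sharpen attribution, but is optional and not needed to resolve the mismatch. What a positive answer on arrival means for that day's session is a clinical matter for the investigators to set, and is not judged here.

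The cost is a change of protocol wording, one extra form field and, as an estimate that the documents do not supply, a minute or two per session. No new instrument, visit or staff is needed.

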**Follow-up (2 hours)**

- All participants will complete outcome measure assessment after completion of the protocol, including re-administration of the Montreal Cognitive Assessment (**MoCA**), Movement Disorder Society-Sponsored Revision of the Unified Parkinson's Disease Rating Scale(**MDS-UPDRS**), 6-minute walk test (**6MWT**), mini-Balance Evaluation Systems Test (**Mini-BESTest**), Functional Gait Assessment (**FGA**), the modified Clinical Test of Sensory Integration and Balance (**mCTSIB**), Delis-Kaplan Executive Functioning System (**DKEFS**), Digit span test (DST), Digit symbol substitution test (DSST), Flanker test, **PROMIS-NeuroQOL**, the Short Form-36 (**SF-36**)
- Prior to follow-up, enrolled participants will receive an email from the study coordinator outlining the requirements of the clinically defined "off" state.

*Participants will be compensated with a \$100 clincard at the conclusion of this visit.*

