**Statistical Analysis:**

To assess feasibility, we will track recruitment rate, retention rate, adverse events, and compliance. We will obtain patient feedback to gather insight about the acceptability and usability of this intervention. We will perform paired t-tests to compare the mean outcome measure values of the treatment and control groups to estimate effect size.

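### Systematic side-effect questions are specified only after treatment sessions, so adverse events after the last session or around the off-medication visits are likely to be under-ascertained

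*Combined protocol and SAP*

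**What the plan says.** All places are in the combined protocol and SAP.

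- **Treatment.** "After each treatment session, participants will be asked post-intervention questions to evaluate potential side effects of the taVNS treatment and exercise". Six questions follow. The first begins "Since our last session, have you experienced any unusual physical symptoms", and the fourth, on mood, also looks back to the previous session. The sixth is the only open item: "Have you experienced any other side effects or symptoms that you believe may be related to the taVNS treatment or exercise program". The section adds "We will also document all reported side effects" and a REDCap tolerability survey. The schedule is "over the course of 4-6 weeks, 1 hour sessions, up to 3 sessions/week".
- **Initial Assessment.** Physical and cognitive tests, quality-of-life questionnaires and a blood draw. No side-effect query is listed.
- **Re-Assessment.** The outcome measures, a REDCap tolerability survey whose content is not shown, and a recorded interview on tolerability and feasibility.
- **Follow-up.** "All participants will complete outcome measure assessment after completion of the protocol". The section lists outcome measures only, with no side-effect question, survey or interview, and does not say how long after Re-Assessment the visit takes place.
- **Inclusion Criteria, note on the off state.** Participants go more than 12 hours without Parkinson's medication. The clinical team supervises and intervenes if it observes adverse effects. No recording step is stated.
- **Statistical Analysis.** "we will track recruitment rate, retention rate, adverse events, and compliance". No definition, collection window or list of sources is given for adverse events.

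**The concern.** Adverse events are one of the four quantities by which the plan judges feasibility. A count of harms depends on when and how people are asked. Here the asking follows the treatment sessions, while two kinds of exposure lie partly outside them: delayed effects after the final session, and medication withdrawal around three assessment visits.

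Falls are the clearest example. A fall in the past 6 weeks rules a person out, a gait belt is used during exercise, and gait and balance tests are run off medication. Yet none of the six questions mentions a fall.

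If the plan is followed exactly, a low adverse-event count would be read as covering the whole study, although for part of it nobody was systematically asked. A later trial might rely on that count.

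**Working it through.** The plan states no adverse-event rate or derived figure on this point, so there is nothing to reproduce. The check is a reading of each visit, plus a count of contacts.

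**1. What is asked at each visit**

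| Visit | Off medication | Six questions | Other tolerability query | Recording of effects stated |
|---|---|---|---|---|
| Initial Assessment | yes | no | none | no |
| Treatment sessions | not stated | yes, after each | REDCap survey | yes, those reported |
| Re-Assessment | yes | no | REDCap survey and interview | no (interview is recorded and transcribed) |
| Follow-up | yes | no | none | no |

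Off-medication visits with the six questions: 0 of 3. Off-medication visits with any tolerability query: 1 of 3.

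**2. Contacts and intervals**

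- Maximum sessions: 3 per week × 4 weeks = 12, up to 3 × 6 = 18.
- Between-session intervals: 12 − 1 = 11, up to 18 − 1 = 17. The look-back in questions 1 and 4 covers these.
- Intervals after the last session: 2. From the last session to Re-Assessment, the only query is the survey and interview. From Re-Assessment to Follow-up, there is none.
- The plan gives the length of neither interval, so the time without systematic questioning cannot be computed.

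**3. What the wording reaches**

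- Questions 1 and 4 look back. Asked after the final session, they cover the interval before it. Symptoms that appear later need a later asking, and these questions are not scheduled again.
- Questions 2, 3, 5 and 6 have no stated look-back. Asked after the final session, they can pick up effects present by then, but not those that develop afterwards.
- Question 6 asks only for symptoms the participant believes are related to taVNS or exercise. It does not invite a report of something attributed to being off medication.
- The withdrawal lasts more than 12 hours and precedes the assessment, so part of it takes place outside the clinic, where staff cannot observe it.

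**4. Link to the analysis**

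Statistical Analysis does not say which sources feed the adverse-event measure. The rule on documenting reported side effects sits under Treatment. It covers what is reported and schedules no asking elsewhere.

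**The case against.** The strongest case on the other side has five parts.

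1. **An unprompted event is not an uncounted event.** A reader might infer that events after the last session, or around the off-medication visits, drop out of the count altogether. The documents do not support that. Statistical Analysis does not restrict the measure to the six questions, the documentation rule has no stated time limit, and off-medication visits are supervised. This stands, and it is why the conclusion is likely under-ascertainment rather than certain omission.
2. **Re-Assessment does ask.** A reader might infer that there is no structured questioning at all from the last session to Follow-up. The tolerability survey and interview contradict that, and since the survey content is not shown, it may include side effects. This stands for treatment-related effects up to Re-Assessment. However, neither source is tied to adverse-event recording, and Follow-up has neither.
3. **Coverage is not confined to gaps between sessions.** Only questions 1 and 4 look back. The other four can also capture effects during and just after a session, including the last one. This stands.
4. **The first look-back may have a referent.** Screening & Informed Consent describes its visit, which includes a 5-minute taVNS trial, as a session, and the off-state note calls the assessments evaluation sessions. So question 1 at the first treatment visit may reach back to one of these. The text does not settle which, so this is an ambiguity and not a proven gap.
5. **SF-36 and NeuroQOL are repeated at Follow-up.** They touch on pain, mood and cognition, and the Questionnaires section sets a notification route for severe depression or risk. They overlap questions 4 and 5 but are not described as adverse-event recording. They also do not ask what is new since the last contact.

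What none of this answers is the absence of any side-effect query at the Initial Assessment and Follow-up, of any item on falls or the off-medication period, and of a recording step for effects observed at off-medication visits.

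**Conclusion.** The point holds as a gap in ascertainment. The plan specifies systematic side-effect questioning only after treatment sessions. Delayed events after the last session, and events around the three off-medication visits, are therefore likely to be under-recorded in the adverse-event measure.

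Its size can be stated only as coverage: 0 of 3 off-medication visits with the six questions, 1 of 3 with any tolerability query, and one of the two post-treatment intervals with no query at all. How many events would be missed is unknown, because the plan gives neither an event rate nor the length of those intervals. The direction is towards too low a count.

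This rests on two assumptions: that the visit lists are complete, and that the tolerability survey is not already an adverse-event form. If the survey does elicit and record adverse events, the gap narrows to the Initial Assessment, Follow-up and the off-medication periods.

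The change should be made. It alters what is collected, so it cannot be repaired at the analysis stage.

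**What to change.** - Ask the side-effect questions once at each of the Initial Assessment, Re-Assessment and Follow-up, with the look-back worded as 'since we last saw you, including today'. Using the same wording at treatment sessions would settle what the first look-back refers to.
- Add an item on falls.
- Make the open question cover any new symptom, including during the off-medication period, whatever the participant believes caused it. Repeating the six questions unchanged would not be enough, because the present open item is limited to taVNS or exercise.
- State that adverse effects observed by staff at off-medication visits are recorded.
- In Statistical Analysis, name the sources that feed the adverse-event measure (questions, survey, interview, staff observation and spontaneous report), and summarise events by arm and by period.

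The cost is a few minutes at three existing visits and a form change. No new visit and no change to treatment or sample size is needed. The reported adverse-event rate may rise. Events after the Follow-up visit itself would still depend on spontaneous report.
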